6.4.4 Other Bleeding Sites

For bleeding sites other than the TBS, the Investigator may use any means necessary to control bleeding, except for any hemostatic products containing thrombin or aprotinin (Thrombin-JMI, Evithrom, Floseal, Tisseel, Evicel, Tachosil, Evarrest). Recothrom should not be used in subjects randomized to receive HEMOBLAST™, but may be used in subjects randomized to the G+T arm.

The Investigator may also use any of the remaining randomized hemostat on these bleeding sites.

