- Subject has a documented severe congenital or acquired immunodeficiency;
- Subject has religious or other objections to porcine, bovine, or human components;
- Subject in whom the investigational or control device will be used at the site of a valve replacement or repair;
- Subject in whom the investigational or control device will be used at the site of a synthetic graft or patch implant;

³ ASA Classification: 1 – normal health patient; 2 – patient with mild systemic disease; 3 – patient with severe systemic disease; 4 – patient with severe systemic disease that is constant threat to life; 5 – moribund patient who is not expected to survive with the operation; 6 – a declared brain-dead patient whose organs are being removed for donor purposes

- Subject is currently participating or has participated in another clinical trial within the past 30 days and is receiving/has received an investigational drug, device, or biologic agent; and
- Subject is not appropriate for inclusion in the clinical trial, per the medical opinion of the Principal Investigator.

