5.6 Point of Enrollment

All patients presenting to the Investigator for elective (non-emergent) open cardiothoracic, abdominal, or orthopedic lower extremity surgical procedures are potential study subjects and should be screened for eligibility. Subjects will need to meet all eligibility in order to be enrolled into the investigation.

A subject is enrolled when he/she meets all preoperative inclusion/exclusion criteria, signs the informed consent forms, and meets the intraoperative inclusion criteria. The point of enrollment into the clinical investigation will occur intraoperatively.

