6.2.2 Preoperative Eligibility

Once written informed consent has been obtained, the Preoperative Eligibility CRF will be completed to document adherence to the preoperative inclusion and exclusion criteria from Section 5.5.

Where a subject fails to fulfill any element of the preoperative eligibility criteria, this will be documented and any signed consent form and completed preoperative inclusion/exclusion criteria retained by the Principal Investigator. The subject will not be advanced any further into this clinical investigation.

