6.4.2 Randomization and Hemostat Application

At the start of each surgical procedure, a single HEMOBLAST™ device and a single G+T device will both be prepared per the respective Instructions for Use (unless the subject is a lead-in subject; all lead-in subjects will have a single HEMOBLAST™ device prepared). The preparation time for both devices will be recorded for the TTH Population subjects.

Randomization will be performed through sequentially numbered sealed envelopes. Four-hundred subjects (TTH Population) will be randomized to receive HEMOBLAST™ or G+T in a 2:1 ratio:

- 267 subjects will be randomized to receive HEMOBLAST™; and
- 133 subjects will be randomized to receive G+T.

There will be a maximum of 50 lead-in subjects; these subjects will not be randomized. The first subject for each investigator will be treated as a lead-in subject. These subjects will receive HEMOBLAST™ and will be followed for safety only (maximum Full Analysis Population of 450); lead-in subjects will not count towards the TTH Population. Please see Section 12 below for additional detail on subject populations.

Randomization will be stratified by surgical indication and will incorporate blocking; additional details of randomization and blocking will be included in a separate Randomization Plan.

After randomization and enrollment, the assigned hemostat will be used in the investigational subject; the other hemostat will be discarded following institutional procedures.

A study-specific stopwatch will be used to track hemostat application and the times of hemostasis evaluation. The time of initial hemostat application will be considered time 0; at this time, the stopwatch will be started by the study coordinator. The stopwatch will run continuously without stopping.

Hemostasis will be evaluated by the investigator at the following time points until hemostasis has been achieved:

- 3 minutes;
- 6 minutes; and
- 10 minutes.

Reapplication of the randomized hemostat will be performed at the 3 minute and 6 minute evaluation time points, as described below.

For cardiothoracic procedures, the TBS will be identified after heparin reversal. Additionally, the TBS will not be at the site of a valve implant or at the site of a synthetic graft or patch implant.

HEMOBLAST™ will be applied according to its instructions for use.

1. Peel open the pouches to remove contents with attention to sterile procedures.
2. Remove cap using a twisting motion.

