3. Blot excess blood from the target bleeding site with gauze/pad or suction so the hemostatic implant material may be applied directly to the source of bleeding. The wound surface should be as dry as possible before application.
4. Apply hemostatic implant material to the source of bleeding by squeezing the bellows. Enough implant material should be applied to cover the entire source of bleeding.
5. Immediately use a wet laparotomy pad to hold the hemostatic material at the target bleeding site using wound appropriate pressure to conform the powder to the source of bleeding.
6. Maintain the hemostatic material at the target bleeding for approximately three minutes. Gently lift the laparotomy pad and inspect the area.
7. If hemostasis has not been achieved, repeat steps 3-6 or use an alternate method of hemostasis treatment.
8. Discard any unused product after opening.

HEMOBLAST™ contraindications include:

- Do not inject directly into the blood vessels.
- Do not apply HEMOBLAST™ Bellows in the absence of active blood flow, e.g., while the vessel is clamped or bypassed. Extensive intravascular clotting and even death may result.
- Do not use HEMOBLAST™ Bellows for treatment of severe or brisk bleeding.
- Do not administer to patients with known allergies or hypersensitivity to materials of porcine or bovine origin.
- To avoid risk of allergic-anaphylactoid reaction and/or thromboembolic events, which may be life-threatening, do not inject HEMOBLAST™ Bellows into a vessel or tissue.
- Do not use in the closure of skin incisions because it may interfere with the healing of the skin edges due to mechanical interposition of the powder.

After randomization, G+T will be applied to the TBS per the Instructions for Use for subjects assigned to this treatment group.

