10 TERMINATION OF THE CLINICAL INVESTIGATION

10.1 Subject Withdrawals and Discontinuation

During the course of this clinical investigation, subjects will be or may elect to withdraw from investigation participation for any of the following reasons:

- Subject's withdrawal of consent;
- Any unexpected adverse device effect which is, in the opinion of the Principal Investigator, related to the device and will endanger the well-being of the subject if the treatment is continued;
- The development of any undercurrent illness(es), infection(s) or condition(s) that might interfere with the Clinical Investigational Plan; or
- Any problem deemed by the Principal Investigator and/or Sponsor to be sufficient to cause discontinuation.

All subjects discontinued from the clinical investigation due to an UADE, directly related to the clinical investigation, will be treated until the effect resolves. The Principal Investigator will clearly document the date and reason(s) for subject withdrawal in Discontinuation CRF.

Subjects who are withdrawn will not be replaced if they have received the investigational or control device. If possible, any procedures or assessments planned for the subject on withdrawal from the clinical investigation should be performed when intention to withdraw the subject is announced.

Subjects who are withdrawn prior to receiving investigational or control device will be replaced.

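### Section 6.4.4 lets leftover randomized hemostat go on any non-target bleeding site and does not carry over the valve and synthetic graft/patch exclusion of Section 5.5.1.2

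*Protocol*

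**What the plan says.** Protocol Section 6.4.4 covers bleeding away from the TBS. It bars other hemostats containing thrombin or aprotinin, naming seven, and bars Recothrom in the HEMOBLAST arm only. It then adds: "The Investigator may also use any of the remaining randomized hemostat on these bleeding sites." No type of site is excepted, and there is no reference back to the exclusion criteria.

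Section 5.5.1.2, repeated in the Synopsis, has two exclusions that bear on this: "Subject in whom the investigational or control device will be used at the site of a valve replacement or repair" and "Subject in whom the investigational or control device will be used at the site of a synthetic graft or patch implant". Both turn on where a device is used; neither mentions the TBS. They are preoperative criteria. Section 6.2.2 states that, after consent, "the Preoperative Eligibility CRF will be completed to document adherence to the preoperative inclusion and exclusion criteria from Section 5.5".

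At the operative stage, Section 6.4.2 says: "Additionally, the TBS will not be at the site of a valve implant or at the site of a synthetic graft or patch implant." The SAP adds no rule about application sites.

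**The concern.** One section rules out a use of the device, and another, read alone, allows it. The section that allows it is the one a surgeon would consult when a second site bleeds and opened study product is at hand.

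What is at stake is patient safety and the consistency of the protocol. The version history shows that the graft and patch exclusion was added in Version 3.0 after a call with FDA, so the sponsor treated it as a deliberate restriction. The documents do not give the reason for it. Section 13.2 lists thrombosis or thromboembolism among the risks possibly related to similar hemostats, but does not link that risk to valves or grafts.

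**Working it through.** No arithmetic applies. The check sets the provisions side by side and asks which of them speaks when leftover product is about to be used.

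| Provision | When it acts | Sites it reaches | Names valve, graft or patch sites? |
|---|---|---|---|
| 5.5.1.2 exclusions | Preoperative screen; must be satisfied at enrollment (5.6) | Any site where either device will be used | Yes |
| 6.4.1 intraoperative criteria | At enrollment | TBS, plus infection at the surgical site | No |
| 6.4.2 sentence on TBS location | When the TBS is chosen | TBS only | Yes |
| 6.4.2 HEMOBLAST contraindications | At application | Any | No (0 of 6 listed) |
| 6.4.4 permission | When product remains | All non-TBS sites | No (0 site limits) |

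1. *Can a patient with a valve or graft be in the trial?* Yes. The exclusions concern device use at those sites, not valve or graft surgery as such. The 6.4.2 sentence on where the TBS may lie would have little purpose if such patients could not be enrolled with a TBS elsewhere.

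2. *Can a bleeding valve or graft site fall under 6.4.4?* Yes. It is a site other than the TBS, and nothing in 6.4.4 removes it.

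3. *When is leftover use decided?* Product can remain only after the assigned hemostat has been applied to the TBS, so the subject is by then enrolled, randomized and treated. Section 5.6 sets the last eligibility checkpoint earlier: "A subject is enrolled when he/she meets all preoperative inclusion/exclusion criteria, signs the informed consent forms, and meets the intraoperative inclusion criteria." At that checkpoint the exclusion can be applied to the proposed TBS. Later use elsewhere can only be predicted.

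4. *What governs that later moment?* Section 6.4.4 permits the use. The 6.4.2 sentence is limited to the TBS. The six listed HEMOBLAST contraindications concern injection into vessels, absence of active blood flow, severity of bleeding ("Do not use HEMOBLAST™ Bellows for treatment of severe or brisk bleeding"), porcine or bovine allergy, injection into vessel or tissue, and skin closure. None names a valve, graft or patch.

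5. *Is the place of leftover use recorded?* Section 6.4.5 lists location under the description of the TBS, and it lists the amount of hemostat applied. No listed item asks where leftover product went.

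6. *Is the primary analysis touched?* No. Section 12.3.1.2 uses one site per subject, the first bleeding site identified.

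The number of subjects affected cannot be estimated. It requires a bleeding valve or synthetic graft/patch site, leftover product, and a decision to use it there. The documents give a frequency for none of these.

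**The case against.** The strongest reply is that the use is already forbidden. Section 5.5.1.2 is worded by device use, so it reaches leftover product, and a specific site rule can be read as limiting the general permission in 6.4.4. That reading is sound and a careful investigator could adopt it. It still has to be inferred: 6.4.4 grants permission in express terms, and the rule that would limit it sits in a preoperative checklist.

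Other safeguards exist. Section 3.5 forbids use outside the plan and requires the Instructions for Use to be followed. Protocol 12.2.8 and SAP 10.11.1 count unapproved departures from eligibility criteria as important deviations. Section 16.2 requires prior sponsor approval for anticipated deviations that affect subject safety. These give real but partial protection, because each first needs someone to recognize the use as contrary to the plan, and 6.4.4 makes that uncertain.

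The Instructions for Use (Appendix A), the control product's instructions, the Investigator Training Plan (Appendix D) and the case report forms were not available. Section 6.4.2 introduces its contraindications as a non-exhaustive list. Any of these documents may already bar the sites in question. This objection stands and limits the point.

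Three stronger readings are tempting but not supported:

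- *That the exclusion lapses once the subject is treated.* Section 10.1 says "Subjects who are withdrawn will not be replaced if they have received the investigational or control device", and Section 11 keeps such subjects' data in the analysis. Those rules govern replacement and data use. They neither permit the use nor lift the restriction.
- *That resulting harm would go unseen.* Section 6.8 records the procedure and reason for any reoperation, not only findings at the TBS. All adverse events are collected, and the Clinical Events Committee described in Section 8 adjudicates every serious adverse event for relation to the hemostat. Operative reports and monitoring (9.2, 16.3) could also reveal such use.
- *That FDA required the rule in 6.4.4, or that thrombosis was the reason.* The version history records only that a preoperative criterion was added, and that criterion is present.

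**Conclusion.** The point holds as a minor safety and consistency correction. Section 6.4.4 permits, without a site limit, a use that Section 5.5.1.2 excludes, and the one operative-stage bar does not extend beyond the TBS. It is more than a missing cross-reference, because an express permission meets a safety exclusion and patients with valves or grafts can be enrolled. It does not show that the use is nowhere prohibited.

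The size is unknown and may be zero subjects. There is no effect on the primary endpoint, alpha, power or sample size. The conclusion rests on the protocol and SAP text alone; the unseen instructions and training plan could reduce its practical importance. Even if they bar these sites, 6.4.4 should not read as allowing them.

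**What to change.** Add one sentence to Section 6.4.4: leftover study hemostat must not be applied where a valve has been replaced or repaired, or where a synthetic graft or patch has been implanted.

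Optionally, add a field to Section 6.4.5 and the Intraoperative CRF for the location of any leftover application. Section 6.4.2 and the intraoperative criteria can stay as they are, since the TBS is already covered by 6.4.2 and by the enrollment rule in 5.6.

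The cost is small. The surgeon must use another permitted method at those sites, and the optional field adds one item to record during surgery. No subject loses eligibility, because the sentence only makes the sponsor's existing restriction explicit at the point of use.

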6.4.5 Intraoperative Data Collection

The following data will be recorded on the Intraoperative CRF:

- Surgical procedure(s);
- Preparation times for each device;
- Description of TBS;
 - Location,
 - Tissue type,
 - Conventional means for hemostasis (pressure, suture, cautery, etc.),
- Confirmation of intraoperative eligibility criteria;
- Approximate dimensions of target bleeding site;
- SBSS score at baseline and each evaluation time point (3, 6, and/or 10 minutes) until hemostasis is achieved;
- Randomization;
 - Randomization envelope number,
 - Time of randomization,
 - Treatment arm and device lot/batch number data,
- Hemostat application;
 - Application amount
 - HEMOBLAST™ application amount will be approximated by indicating the amount of powder left in the bellows after application
 - G+T application amount will be documented by approximating the dimensions of Surgifoam sponge applied
- Rescue treatment(s), if any;
- Use of other hemostatic agent(s), if any;
- Skin open and skin closure times;
- Intraoperative administration of blood products;
- Total intraoperative estimated blood loss;
- Incidence of any device deficiencies; and

- Incidence of any complications or adverse events.

The Concomitant Medication, Adverse Event, and Device Deficiency CRFs will be completed as applicable.

Table 7 below shows a timeline of intraoperative procedures.

Table 7. Timeline for Intraoperative Procedures*

Time Point (Minutes:Seconds)	Study Procedures or Assessments
Prior to 00:00	
 • Prepare both hemostatic devices and record time of preparation • Identify Target Bleeding Site (TBS) • Assign SBSS score • Perform randomization (unless lead-in subject)
00:00	
 • Start stop-watch • Apply HEMOBLAST™ or G+T
03:00	
 • Assign SBSS score 
If SBSS = 0
 
 • Intraoperative efficacy evaluation completed 
If SBSS is NOT 0
 
 • Re-apply HEMOBLAST™ or G+T
06:00	
 • Assign SBSS score 
If SBSS = 0
 
 • Intraoperative efficacy evaluation completed 
If SBSS is NOT 0
 
 • Re-apply HEMOBLAST™ or G+T
10:00	
 • Assign SBSS score 
If SBSS = 0
 
 • Intraoperative efficacy evaluation completed 
If SBSS is NOT 0
 
 • Rescue treatment

* Assuming subject meets all intraoperative eligibility criteria

The Concomitant Medication, Reoperation, and Adverse Event CRFs will be completed as applicable.

6.5 Postoperative Procedures and Evaluations

All subjects will undergo the following assessments within 24 hours postoperatively, which will be recorded on the Postoperative CRF:

- CBC (Laboratory CRF);
- Postoperative visit date;
- Coagulation status (Laboratory CRF);
- Chemistry panel (Laboratory CRF);
- Clinical signs or symptoms of bleeding;

- Any administration of blood products;
- Incidence of reoperation for bleeding; and
- Incidence of any complications or adverse events.

The Laboratory CRF will be completed and the Concomitant Medication, Reoperation, and Adverse Event CRFs will be completed as applicable.

6.6 Follow-Up Procedures and Evaluations

All subjects will undergo the following assessments 6 weeks \pm 2 weeks postoperatively, which will be recorded on the Follow-Up CRF:

- Date of hospital discharge;
- Signs or symptoms of bleeding;
- Blood draw for antibody testing;
- Incidence of reoperation for bleeding; and
- Incidence of any complications or adverse events.

The Concomitant Medication, Reoperation, and Adverse Event CRFs will be completed as applicable. A blood draw for antibody testing will be performed and handled per specified procedures agreed upon with the investigational site and core laboratory.

6.7 Discontinuation Procedures and Documentation

The Discontinuation CRF should be completed in the following cases:

- Subject has completed the 6 week follow up;
- Subject withdrawal;
- Subject death; or
- Subject loss to follow-up.

The reason for discontinuation and the date of discontinuation will be noted on the Discontinuation CRF.

6.8 Reoperation Documentation

In cases of reoperation, the following evaluations will be recorded on the Reoperation CRF:

- Date of reoperation;
- Description of surgical procedure;
- Reason for reoperation; and
 - If for bleeding, an Adverse Event CRF will need to be completed
- Previous target bleeding site assessments, if able; and
 - If hemostat (HEMOBLAST™ or G+T) is visually present,
 - If the site is still bleeding,
 - Any other significant findings (e.g., infection, adhesion, etc.).

7 ADVERSE EVENTS

7.1 General

An adverse event (AE) is defined according to the European Standard EN ISO 14155 as ‘any untoward medical occurrence in a subject’. An adverse event related to a device is defined as an ‘adverse device effect’ (ADE) and is defined as ‘any untoward and unintended response to an investigational medical device’.

An adverse event or an adverse device effect may be mild, moderate or severe and are usually unexpected.

A device deficiency is defined as the inadequacy of a medical device with respect to its identity, quality, durability, reliability, safety or performance, which may include device malfunctions, use errors and inadequate labeling.

All adverse events, adverse device effects, and or device deficiencies, either observed by the Principal Investigator or reported by the subject, must be reported to the Sponsor/Sponsor representative. To report an adverse event or adverse device effect or device deficiency, the Principal Investigator will complete an adverse event report form or relevant form located in the Case Report Form. The report will include the following information: nature, severity, date of onset, duration, course and history of the adverse event/adverse device effect and causality. The subject will be questioned about any adverse event(s) and adverse device effect(s) at each visit.

Expected adverse events and anticipated adverse device effects are included in Section 13.

7.2 Adverse Event Documentation

Adverse events will be documented by the Principal Investigator on the appropriate source document(s) at the investigational site and also on the Adverse Event CRF. Adverse events are to be recorded and dated according to when they are first observed. The subsequent treatment(s) should also be documented. The following will be recorded on the Adverse Event CRF:

- Accepted medical term for the event;
- Description of the event;
- Date of onset;
- Date of resolution, if applicable;
- Outcome;
- Treatment(s)/action(s) taken;
- Severity;
- Relationship to the investigational device; and
- Determination of reportability (see Reporting Section below).

The severity of the event will be determined by the Principal Investigator using the following definitions:

- Mild: the symptoms are transient, barely perceptible by the subject and do not hinder normal activity; no treatment is usually prescribed to reduce these symptoms;
- Moderate: the symptoms are sufficiently severe to provoke discomfort in the subject and sufficiently uncomfortable to prevent normal activity; a treatment may be required; or
- Severe: the symptoms considerably modify the normal course of the subject’s activities or are disabling or are life-threatening; the treatment studied should be suspended; a treatment for the symptoms is prescribed.

The relationship to the investigational device will be determined by the Principal Investigator using the following definitions:

- Not related: the adverse event is due to the underlying disease state or is due to concomitant medications or therapy not related to the use of the device;
- Possibly related: the adverse event has a reasonable temporal relationship to the use of the device but alternative etiology is equally or more likely compared to the potential relationship to the use of the device;
- Probably related: the adverse event has a strong temporal relationship to the use of the device and alternative etiology is less likely compared to the potential relationship to the use of the device; or
- Definitely related: the adverse event has a strong temporal relationship to the use of the device, follows a known response pattern and cannot reasonably be explained by known characteristics of the subject's clinical state or other therapies.

The expectedness of the adverse event will be determined by the Principal Investigator as:

- Anticipated; or
- Unanticipated.

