6.4 Intraoperative Procedures and Evaluations

All subjects will undergo the same intraoperative investigational evaluations. Intraoperative is defined as the time interval from when the subject enters the surgical suite until the subject exits the surgical suite.

Subjects undergoing the open elective cardiothoracic, abdominal, and orthopedic lower extremity surgeries are eligible for enrollment into the clinical investigation. The Investigator will perform the surgery per his or her standard procedures, including conventional methods of hemostasis (pressure, ligation, cautery, etc.).

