12.1.3 Safety Outcomes

Endpoints used to characterize the safety profile include the rate of occurrence of all AEs and SAEs, reoperation rate due to bleeding, mean volume of intraoperative transfusions, total operative time, mean duration of hospitalization, intraoperative blood product administration, and post-operative blood product administration.

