Intraoperative Time	Time from skin open to skin closure
IRB	Institutional Review Board
QA	Quality Assurance
Relationship (of an adverse event to the investigational device)	
 • Not related: the adverse event is due to the underlying disease state or is due to concomitant medications or therapy not related to the use of the device • Possibly related: the adverse event has a reasonable temporal relationship to the use of the device but alternative etiology is equally or more likely compared to the potential relationship to the use of the device • Probably related: the adverse event has a strong temporal relationship to the use of the device and alternative etiology is less likely compared to the potential relationship to the use of the device • Definitely related: the adverse event has a strong temporal relationship to the use of the device, follows a known response pattern and cannot reasonably be explained by known characteristics of the subject's clinical state or other therapies
SADE	Serious Adverse Device Effect – an adverse device effect that has resulted in any of the consequences characteristic of a serious adverse event or that might have led to any of these consequences if suitable action had not been taken or intervention had not been made or if circumstances had been less opportune
SAE	Serious Adverse Event – an adverse event that: 
 • Led to death • Led to a serious deterioration in the health of the subject, that either resulted in a life-threatening illness or injury, or a permanent impairment of a body structure or a body function, or in-patient hospitalization or prolongation of existing hospitalization, or resulted in medical or surgical intervention to prevent life-threatening illness or injury or permanent impairment to a body structure or a body function •
SBSS	Surface Bleeding Severity Scale

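### Adverse events before hemostat application are counted in the arm rates, and the listed CRF fields give no onset time to set them apart, so subject-level safety comparisons are attenuated

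*Protocol*

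**What the plan says.** Exposure starts during surgery. Protocol 5.6 states: "The point of enrollment into the clinical investigation will occur intraoperatively". Protocol 6.4.2 sets the clock: "The time of initial hemostat application will be considered time 0". SAP 8.2 places randomization immediately before treatment.

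The period for intraoperative events starts earlier. Protocol 6.4 reads: "Intraoperative is defined as the time interval from when the subject enters the surgical suite until the subject exits the surgical suite". Protocol 17 defines intraoperative time differently, as "Time from skin open to skin closure". Both starting points precede application. The Intraoperative CRF (Protocol 6.4.5) collects "Incidence of any complications or adverse events" with no limit to events after application, and the CRF schedules (Protocol Table 5, SAP Table 2) make the AE form available in the intraoperative column.

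On timing, Protocol 7.2 says: "Adverse events are to be recorded and dated according to when they are first observed". Its list of AE form items has dates of onset and resolution, but no clock time and no marker relative to application. The exception is a re-bleed before closure, whose time of observation is recorded (Protocol 6.4.3); that event can only follow application.

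On analysis, the safety endpoints include "the rate of occurrence of all AEs and SAEs" (Protocol 12.1.3, repeated in SAP 10.6.2). Protocol 12.3.2.2 and SAP 10.6.2 summarize AEs by arm and compare between arms the proportion of subjects with SAEs. Neither document defines a treatment-emergent event. The safety population includes the lead-in subjects.

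**The concern.** An event during anesthesia, incision or bypass, before any hemostat touches the patient, cannot be an effect of either product. Under the plan it still enters that subject's arm. In a subject-level proportion, someone with an earlier event is already counted, so a later device-caused event adds nothing. Any true difference between arms, in either direction, is pulled toward zero. In a trial whose objective includes the safety of a new device, attenuation toward no difference is the uncomfortable direction. All events on the day of surgery share one date, so the recorded onset cannot show which came first.

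**Working it through.** **Denominator.** The plan gives a maximum safety population of 450: 267 + 133 + 50 = 450. By product received, that is 267 + 50 = 317 HEMOBLAST and 133 G+T. The documents give no AE or SAE rates and no power for safety, so all rates below are assumptions.

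**Can the listed fields order an event against application?**
- AE form: date of onset, which is day 0 on both sides of application.
- Intraoperative CRF: "Time of randomization", which gives a clock anchor for randomized subjects only, with no AE clock time to compare with it.
- First application: stopwatch zero, with no clock time among the listed items.

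The answer is no.

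**Dilution.** Let q be the share of subjects with at least one qualifying event before application, equal in the two arms and independent of later events. Let p be the post-application rate.

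- Observed proportion = q + (1 − q)p
- Observed difference = (1 − q)(p_H − p_G)

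Assume p_H = 50% and p_G = 40%. SE = √[a(1 − a)/317 + b(1 − b)/133], with a and b the observed proportions. Power at two-sided 0.05 is approximately Φ(difference/SE − 1.96).

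| q | Observed H vs G+T | Difference (points) | SE (points) | Difference/SE | Power |
|---|---|---|---|---|---|
| 0 | 50% vs 40% | 10 | 5.09 | 1.964 | 50% |
| 10% | 55% vs 46% | 9 | 5.15 | 1.749 | 42% |
| 20% | 60% vs 52% | 8 | 5.13 | 1.559 | 34% |
| 30% | 65% vs 58% | 7 | 5.05 | 1.386 | 28% |

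**A less common outcome.** SAEs are likely to have lower rates and a lower q. With assumed rates of 13% and 5%, the same formula gives 85% at q = 0, 80% at 1%, 75% at 2% and 62% at 5%. At q = 5%, for example, the comparison is 17.35% vs 9.75%, a difference of 7.6 points with SE 3.34. A pooled null variance in the test lowers these to 74%, 70%, 65% and 54%; the pattern is the same.

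**Lead-ins.** Up to 50 of the 317 HEMOBLAST subjects (15.8%) are not randomized. If their pre-device share is q_L, the HEMOBLAST background is (267q + 50q_L)/317, which departs from q by 0.158(q_L − q). A 10-point gap between q_L and q would shift that arm by 1.6 points. If q_L = q, the background proportion does not shift, although the events still add to that arm's count.

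**The case against.** Five points deserve weight.

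1. *The start of AE collection is inferred.* No sentence states it. Collection from enrollment is a possible reading, since a subject is enrolled only when the intraoperative criteria are met, and few events would then precede application. This stands as a caution. But the only written definitions of the period start earlier, and the two differ, so sites could apply either.

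2. *A reader might infer that no later analysis could remove these events.* The documents do not support that. The AE report covers course and causality (Protocol 7.1), the form has a description and relatedness (7.2), source records include operative reports (9.2), the events committee adjudicates SAEs for relatedness (section 8), and the SAP reports UADEs and SADEs separately. Since every related category requires a temporal link to device use, device-attributed results are largely protected. What remains is that such separation is partial and post hoc, and none of it restricts the all-event rates.

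3. *A reader might infer that HEMOBLAST's rate is inflated relative to control.* In randomized subjects, events before application arise essentially before allocation. They raise both arms alike in expectation. Only the lead-ins act on one arm.

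4. *A reader might infer that a planned between-arm AE test loses power.* For AEs the plan specifies summaries by arm; the explicit AE-type comparison is of SAE proportions. If AEs are tallied as events, an equal background does not shrink the difference. The (1 − q) factor applies to subject-level proportions, and for SAEs q is probably small, because it requires a serious event in someone who is then still enrolled.

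5. *The eCRFs are not among the documents.* Protocol 7.3 mentions a separate SAE eCRF whose fields are not listed; it may hold an onset time. The finding is limited to the fields the protocol lists.

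**Conclusion.** The point holds in a bounded form. As the plan is written, day-0 events before application count in the AE and SAE rates by arm, and the listed CRF fields cannot place them before or after application. The consequence is attenuation of subject-level proportions by (1 − q), mainly in the SAE comparison, together with a possible one-arm contribution from lead-ins. It is not a demonstrated imbalance between randomized arms, and the events are not beyond any recovery.

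The size cannot be derived from the documents. The power figures illustrate direction and scale only; they rest on assumed rates, equal q in both arms and independence of earlier and later events. Restricting the analysis to events at or after application would restore the q = 0 row. This is an inexpensive improvement worth making, because onset order is easy to record at the time and not reliably recoverable from the listed fields afterwards.

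**What to change.** - Add one field to the AE and SAE forms for day-0 events: onset before, or at or after, first hemostat application (stopwatch zero). Complete it for lead-in subjects too.
- In Protocol 12.3.2.2 and SAP 10.6.2, base the AE and SAE summaries and the between-arm SAE comparison on events with onset at or after first application. List earlier events separately, so that nothing is lost from the record.
- State when AE collection starts, and reconcile the two definitions of the intraoperative period in Protocol 6.4 and Protocol 17.

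The cost is one CRF field, a few sentences in the protocol and SAP, and minor site effort for day-0 events. Sample size and the efficacy analysis are unaffected.
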